8.4 Dose Modifications of Dexamethasone during a Cycle of Therapy

CTCAE System/organ/Class (SOC)	ADVERSE EVENT	AGENT	ACTION ** (each cycle)
Gastrointestinal Disorders	Dyspepsia, gastric or duodenal ulcer, gastritis Grade 1-2 (Symptomatic; altered GI function; medical intervention indicated; limiting instrumental ADL)	Dexamethasone	Treat with H2 blockers, sucralfate, or omeprazole If symptoms persist despite above measures, decrease dexamethasone dose by 50%
	Dyspepsia, gastric or duodenal ulcer, gastritis ≥Grade 3 (Severely altered GI function; TPN indicated; elective operative or endoscopic intervention indicated; limiting self-care ADL; disabling)		Omit dexamethasone until symptoms adequately controlled Restart one dose level below along with concurrent therapy with H2 blockers, sucralfate, or omeprazole If symptoms persist despite above measures, decrease dex by 50%
	Pancreatitis ≥Grade 3 (severe pain; vomiting; medical intervention indicated (e.g., analgesia, nutritional support))		Discontinue dex, and begin event monitoring
General Disorders	Edema ≥Grade 3 (limiting function and unresponsive to therapy or anasarca)		Decrease dex by 50%; use diuretics prn
Psychiatric Disorders	Confusion or Mood alteration ≥Grade 2 (Severe disorientation; limiting self-care ADL)		Omit until symptoms resolve; Decrease dex by 50%
Musculoskeletal and connective tissue disorders	Muscle weakness ≥Grade 2 Weakness limiting self-care ADL; disabling		Decrease dex by 50%; if symptoms persist then decrease 50% prn
Eye Disorders	Blurred vision ≥Grade 3		Decrease dex by 50%; if symptoms persist then decrease 50% prn
Metabolism and nutrition disorders	Hyperglycemia Grade 3 or higher, (>250 - 500 mg/dL; >13.9 - 27.8 mmol/L); hospitalization indicated	Treat with oral hypoglycemic agent or insulin prn; decrease by 50% prn	

* Located at http://ctep.cancer.gov/protocolDevelopment/electronic_applications.ctc.htm

** Use the following to describe actions in the Action column:

- Omit = The current dose(s) for the specified drug(s) during a cycle is skipped. The patient does not make up the omitted dose(s) at a later time
- Hold/Delay = The current dose(s) of all drugs during a cycle is delayed. The patient does make up the delayed dose(s) when the patient meets the protocol criteria to restart drugs.
- Discontinue = The specified drug(s) are totally stopped.

NOTE: If the patient experiences a significant adverse event requiring a dose reduction at the start of the next cycle, then the dose will remain lowered for that entire subsequent cycle. If that cycle is

completed with no further adverse events >Grade 2, then the dose may be increased, at the investigator's discretion, one level at a time, in the following cycles.

NOTE: Adverse events requiring a dose-reduction step for any or all drugs beyond the two dose-reduction steps (levels –1 and –2) will be at the discretion of the treating physician, if the decision is made for the patient to be kept on study. These dose reductions must be clearly recorded in reported clinical data.

NOTE: Patients in whom one or more of the study treatment agents have been discontinued will remain on study unless all study treatment agents are discontinued. Patients in whom all study treatment agents were discontinued will proceed to event monitoring (see [Section 18.0](#)).

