7.22 Definition of DLT – See Section 16.22 for additional information

For this protocol, DLT will be defined as an adverse event during Cycle 1 of treatment at least possibly related to the study medication and meeting the following criteria:

Toxicity*	DLT Definition
Blood and lymphatic system disorders	Grade 3 Febrile neutropenia: ANC <1000/mm ³ with a single temperature of >38.3 degrees C (101 degrees F) or a sustained temperature of ≥38 degrees C (100.4 degrees F) for more than one hour
Investigations	Grade 4 neutropenia (ANC <500/mm ³) for ≥7 days or Grade 4 thrombocytopenia (<25,000/mm ³) for ≥7 days
Infection and infestations	Grade 4
Other Non-hematologic	Grade 4 as per NCI Common Terminology Criteria for Adverse Events v 4.0**
Dose Delay	Any toxicity that causes a dose delay of >2 weeks of the next intended dose.***
Dose Reduction	Any dose reduction within cycle 1.***

*Adverse event at least possibly related to the study medication.

**Grade 4 vomiting or diarrhea with maximal supportive treatment(s) will be considered dose limiting.

***Except dose reductions and delays due to rash associated with lenalidomide. These patients will be replaced with another study patient.

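### Two dexamethasone rows of Table 8.4 are labelled ≥Grade 2 but describe a severity that the same table places at ≥Grade 3, so the action for a Grade 2 event is unclear

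*Combined protocol and SAP*

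**What the plan says.** Section 8.4 gives the dexamethasone modifications by adverse event. Two rows matter here.

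- Psychiatric: "Confusion or Mood alteration ≥Grade 2 (Severe disorientation; limiting self-care ADL". The action is to stop dexamethasone for a time and then halve it: "Omit until symptoms resolve; Decrease dex by 50" percent.
- Musculoskeletal: "Muscle weakness ≥Grade 2 Weakness limiting self-care ADL; disabling". The action is "Decrease dex by 50%; if symptoms persist then decrease 50% prn".

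The gastrointestinal rows of the same table show how it links severity text to grade. The Grade 1-2 row ends "medical intervention indicated; limiting instrumental ADL". The ≥Grade 3 row ends "elective operative or endoscopic intervention indicated; limiting self-care ADL; disabling".

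Section 8.0 makes the modifications strict for the first two cycles and treats them as guidelines after that. Section 8.2 tells the reader to grade by CTCAE version 4.0 unless something else is specified; the footnote to that instruction stands under Table 8.4.

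For Phase I, Section 7.22 lists as a DLT "Any dose reduction within cycle 1", provided that the event is at least possibly related to the study medication. The line names no drug. Its only exemption is for reductions and delays caused by lenalidomide rash. Non-hematologic events outside the infection class are DLTs by grade only at Grade 4.

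**The concern.** A modification table is meant to lead different investigators to the same action for the same event. In these two rows the label and the description set different entry points. By the label, a Grade 2 event is enough. By the description, read on the scale that the gastrointestinal rows use, the event has to reach Grade 3. During the two strict cycles the investigator has no stated discretion to settle the difference, and nothing says which element governs.

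What is at stake in both phases is whether dexamethasone is halved after a Grade 2 mood or weakness event. Section 15.27 lists personality changes, psychosis and muscle weakness among the drug's known toxicities, so the rows are not remote. In Phase I there is a second consequence. The reading can decide whether the patient enters the DLT count, and under Sections 16.21 and 16.224 two DLTs among six patients mean that the MTD has been exceeded.

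**Working it through.** This is a comparison of texts. The plan has no figure for it to reproduce.

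**Step 1. Label against description in Table 8.4.**

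| Row | Grade label | Functional limit in the text |
|---|---|---|
| Dyspepsia, ulcer, gastritis (lower row) | Grade 1-2 | Instrumental activities |
| Dyspepsia, ulcer, gastritis (upper row) | ≥Grade 3 | Self-care; disabling |
| Confusion or mood | ≥Grade 2 | Self-care; called severe |
| Muscle weakness | ≥Grade 2 | Self-care; disabling |

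The last two rows carry the text of the second row with a label one grade lower.

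**Step 2. What each reading requires.** Take an event in Cycle 1 of Phase I that is at least possibly related, with a dexamethasone dose still due and given in that cycle.

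| Grade | By the label | By the description | DLT status differs? |
|---|---|---|---|
| 1 | No action | No action | No |
| 2 | Halve: a Cycle 1 reduction, so a DLT under 7.22 | Row not met; below Grade 4, so not a DLT | Yes |
| 3 | Halve: DLT | Halve: DLT | No |
| 4 | Halve: DLT, also by grade | Same | No |

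Only Grade 2 separates the readings. In Phase II, and in Cycle 2 of Phase I, the treatment difference remains but there is no DLT decision.

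**Step 3. Limits on the DLT consequence.**

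- Dexamethasone is given on Days 1, 8, 15 and 22 (Section 7.11). The first reduced dose within Cycle 1 can fall only on Day 8, 15 or 22. An event after the Day 22 dose affects Cycle 2.
- The mood row omits dexamethasone first. If symptoms last past Day 22, Cycle 1 contains omitted doses but no halved dose. Section 7.22 does not say whether an omission is a reduction.
- Section 7.22 does not define study medication. Dexamethasone is in the Section 7.11 treatment table, so the plain reading includes it.
- An investigator who followed the description but lowered the dose anyway would also meet the 7.22 line.

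**Step 4. Link to the replacement rule.** Sections 13.6 and 16.226 replace a patient whose dose falls below 70% of that expected in Cycle 1 for reasons other than DLT. They do not say for which drug, or whether the 70% applies to a single dose or to the cycle total.

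- Single dose: halving gives 50%, below 70%.
- Cycle total, halved from Day 8: (1 + 3 × 0.5)/4 = 62.5%, below 70%.
- Cycle total, halved from Day 15: (2 + 2 × 0.5)/4 = 75%, above 70%.
- Cycle total, halved from Day 22: (3 + 0.5)/4 = 87.5%, above 70%.

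A dexamethasone reduction that was not called a DLT may therefore lead to replacement or leave the patient evaluable. Together with Step 2, a Grade 2 event in these rows could be recorded as a DLT, as a replaced patient, or as an evaluable patient without DLT.

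**The case against.** **The label is a workable default.** Section 8.2 points to CTCAE grades, and descriptive text in Table 8.4 does not always span its label: the hyperglycemia row is for Grade 3 or higher but gives a range that stops at 500 mg/dL. Text may therefore illustrate without narrowing. The functional anchors are also inferred from the gastrointestinal rows, and no section says that they carry over to psychiatric or muscle terms. This makes the label reading the more natural one for some readers, but it does not remove the conflict. In the hyperglycemia row the text is short at the top of the range. In the two disputed rows it bears on the entry point, which decides whether anything is done.

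**Phase I treatment is over.** The Addendum 5 notes in the Phase I schema and Sections 13.0 and 18.0 take all Phase I patients off study treatment. This stands. Rewording now changes no future DLT decision, and the Phase I interest is in classification and reporting.

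**Counting dexamethasone reductions is legitimate.** Objective 2.11 seeks the anakinra dose that can be combined with the other two drugs, and the authors wrote one exemption deliberately. This also stands. A reader might infer that dexamethasone-driven reductions should not be DLTs; the documents leave that as a design choice.

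**Sites.** A reader might infer that different sites would treat the same event differently in Phase I. Section 6.32 has treatment start at one center and 7.212 rules out local physicians. The inconsistency would be between investigators or occasions. Section 7.214 brings the Study Chair in for recognized DLTs, but not for an event that the investigator reads as requiring no action.

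**Conclusion.** The inconsistency is real and internal to Table 8.4; no outside grading text is needed to see it. It covers two rows and one grade. For a Grade 2 mood or weakness event in the first two cycles of either phase, the table both requires and does not require a 50% dexamethasone reduction. The conclusion assumes only that the table uses its functional descriptions consistently from row to row.

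The DLT consequence follows from 7.22 but is narrow: a related event, exactly Grade 2, with a dexamethasone dose still due in Cycle 1. It is now mainly retrospective.

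Two stronger readings are not supported. One is that the chance of dose escalation falls by a stated amount. The table in 16.227 is correct: (1-p)³ + 3p(1-p)⁵ gives 0.906, 0.709, 0.494, 0.309 and 0.172 for DLT rates of 10 to 50%, matching the plan after rounding. Applying it here would need the share of patients whose DLT status turns on this reading, and the documents give none. A calculation for all dexamethasone reductions would measure the 7.22 rule and not the mismatch. The other is that persistent Grade 1-2 dyspepsia is a further instance. Label and text agree in that row, so it shows no mismatch.

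**What to change.** The clinical team should make the grade label and the severity text agree in the confusion/mood and muscle-weakness rows of Table 8.4. This review does not say which of the two is right.

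For Phase I, list every Cycle 1 dexamethasone reduction or omission with its event, grade, attribution and day. Confirm that each was handled consistently under 7.22 (DLT) and 13.6/16.226 (replacement), and state in the report the convention that was used.

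The cost is a few words in two table rows and one listing. Section 16.12 plans at most 18 + 2 = 20 Phase I patients, so the record check is short. Sample size and the Phase II analysis are unaffected.

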9.0 Ancillary Treatment/Supportive Care

- 9.1 Patients may receive concurrent treatment with a bisphosphonate.
- 9.2 Patients may continue on low level/stable steroid doses for replacement or inhalation therapy.
- 9.3 The following medications are not permitted during the trial:
 - Any other investigational treatment
 - Any cytotoxic chemotherapy
 - Any other systemic anti-neoplastic therapy including, but not limited to, immunotherapy, hormonal therapy or monoclonal antibody therapy.
 - Any external beam radiotherapy
- 9.4 Antiemetics may be used at the discretion of the attending physician.
- 9.5 Blood products and growth factors should be utilized as clinically warranted and following institutional policies and recommendations. ASCO 2006 Update of Recommendations for the Use of White Blood Cell Growth Factors: An Evidence-Based Clinical Practice Guidelines Journal of Clinical Oncology 2006; 24:3187-3205.
- 9.6 Patients should receive full supportive care while on this study. This includes blood product support, antibiotic treatment, and treatment of other newly diagnosed or concurrent medical conditions. All blood products and concomitant medications such as antidiarrheals, analgesics, and/or antiemetics received from the first day of study treatment administration until 30 days after the final dose will be recorded in the medical records.
- 9.7 Diarrhea: This could be managed conservatively with loperamide. The recommended dose of loperamide is 4 mg at first onset, followed by 2 mg every 2-4 hours until diarrhea free (maximum 16 mg/day).

In the event of grade 3 or 4 diarrhea, the following supportive measures are allowed: hydration, octreotide, and antidiarrheals.

If diarrhea is severe (requiring intravenous rehydration) and/or associated with fever or severe neutropenia (grade 3 or 4), broad-spectrum antibiotics must be prescribed. Patients with severe diarrhea or any diarrhea associated with severe nausea or vomiting **should be hospitalized** for intravenous hydration and correction of electrolyte imbalances.
- 9.8 Use of colony stimulating factors is allowed as detailed in the dose modification table for lenalidomide

10.0 Adverse Event (AE) Reporting and Monitoring

10.1 Adverse Event Characteristics

CTCAE term (AE description) and grade: The descriptions and grading scales found in the revised NCI Common Terminology Criteria for Adverse Events (CTCAE) version 4.0 will be utilized for AE reporting. All appropriate treatment areas should have access to a copy of the CTCAE version 4.0. A copy of the CTCAE version 4.0 can be downloaded from the CTEP web site:

(http://ctep.cancer.gov/protocolDevelopment/electronic_applications/ctc.htm)

10.11 Adverse event monitoring and reporting is a routine part of every clinical trial. First, identify and grade the severity of the event using the CTCAE version 4.0. Next, determine whether the event is expected or unexpected (see Section 10.2) and if the adverse event is related to the medical treatment or procedure (see Section 10.3). With this information, determine whether the event must be reported as an expedited report (see Section 10.4). **Important:** Expedited adverse event reporting requires submission of a MedWatch 3500A report(s). Expedited reports are to be completed within the timeframes and via the mechanisms specified in Sections 10.4. All AEs reported via expedited mechanisms must also be reported via the routine data reporting mechanisms defined by the protocol (see Sections 10.52 and 18.0).

10.12 Each CTCAE term in the current version is a unique representation of a specific event used for medical documentation and scientific analysis and is a single MedDRA Lowest Level Term (LLT). Grade is an essential element of the Guidelines and, in general, relates to **severity** for the purposes of regulatory reporting to NCI.

NOTE: A severe AE, as defined by the above grading scale, is **NOT** the same as serious AE which is defined in the table in Section 10.4.

10.2 Expected vs. Unexpected

- The determination of whether an AE is expected is based on the agent-specific information provided in Section 15.0 of this protocol.
- Unexpected AEs are those not listed in the agent-specific information provided in Section 15.0 of this protocol.

NOTE: “Unexpected adverse experiences” means any adverse experience that is neither identified in nature, severity, or frequency of risk in the information provided for IRB review nor mentioned in the consent form.

10.3 Assessment of Attribution

When assessing whether an adverse event is related to a medical treatment or procedure, the following attribution categories are utilized:

Definite - The adverse event *is clearly related* to the agent(s).

Probable - The adverse event *is likely related* to the agent(s).

Possible - The adverse event *may be related* to the agent(s).

Unlikely - The adverse event *is doubtfully related* to the agent(s).

Unrelated - The adverse event *is clearly NOT related* to the agent(s).

Events determined to be possibly, probably or definitely attributed to a medical treatment suggest there is evidence to indicate a causal relationship between the drug and the adverse event.

10.4 Expedited Reporting Requirements for Studies using Commercial Agent(s) ONLY:

Expedited Reporting Requirements for Adverse Events that Occur in a Non-IND/IDE trial within 30 Days of the Last Administration of a Commercial Imaging Agent^{1,2}

FDA REPORTING REQUIREMENTS FOR SERIOUS ADVERSE EVENTS (21 CFR Part 312) NOTE: Investigators MUST immediately report to the sponsor ANY Serious Adverse Events, whether or not they are considered related to the investigational agent(s)/intervention (21 CFR 312.64) An adverse event is considered serious if it results in ANY of the following outcomes:
 
 1) Death 2) A life-threatening adverse event 3) An adverse event that results in inpatient hospitalization or prolongation of existing hospitalization for ≥ 24 hours 4) A persistent or significant incapacity or substantial disruption of the ability to conduct normal life functions 5) A congenital anomaly/birth defect. 6) Important Medical Events (IME) that may not result in death, be life threatening, or require hospitalization may be considered serious when, based upon medical judgment, they may jeopardize the patient or subject and may require medical or surgical intervention to prevent one of the outcomes listed in this definition. (FDA, 21 CFR 312.32; ICH E2A and ICH E6). 				

ALL SERIOUS adverse events that meet the above criteria MUST be immediately reported to the sponsor within the timeframes detailed in the table below.
				
Hospitalization	Grade 1 Timeframes	Grade 2 Timeframes	Grade 3 Timeframes	Grade 4 & 5 Timeframes
Resulting in Hospitalization ≥24 hrs	7 Calendar Days			24-Hour 3 Calendar Days
Not resulting in Hospitalization ≥ 24 hrs	Not required		7 Calendar Days	

NOTE Protocol specific exceptions to expedited reporting of serious adverse events are found in section 10.41 of the protocol.
 
Expedited AE reporting timelines are defined as:
 
 ○ “24-Hour; 3 Calendar Days” - The AE must initially be reported via MedWatch within 24 hours of learning of the AE, followed by a complete expedited report within 3 calendar days of the initial 24-hour report. ○ “7 Calendar Days” - A complete expedited report on the AE must be submitted within 7 calendar days of learning of the AE. 				

¹Serious adverse events that occur more than 30 days after the last administration of investigational agent/intervention and have an attribution of possible, probable, or definite require reporting as follows: Expedited 24-hour notification followed by complete report within 3 calendar days for:
 
 • All Grade 4, and Grade 5 AEs 
Expedited 7 calendar day reports for:
 
 • Grade 2 adverse events resulting in hospitalization or prolongation of hospitalization • Grade 3 adverse events 
² For studies using PET or SPECT IND agents, the AE reporting period is limited to 10 radioactive half-lives, rounded UP to the nearest whole day, after the agent/intervention was last administered. Footnote “1” above applies after this reporting period.
 
Effective Date: May 5, 2011
				

Additional Instructions:

1. An increased incidence of an expected adverse event (AE) is based on the patients treated for this study at their site. A list of known/expected AEs is reported in the package insert or the literature, including AEs resulting from a drug overdose.
2. Submit form 3500A to the FDA, MedWatch, [REDACTED]

Mayo Clinic Cancer Center (MCCC) Institutions: Use MCCC SAE Reporting Form

[REDACTED]
 Provide copies of MedWatch and SOBI SAE forms to the MCCC Regulatory Affairs Unit (RAU) Risk Information Specialist [REDACTED] who will determine and complete IRB reporting. The RAU will submit to the MCCC SAE Coordinator.

10.41 Special Situations for Expedited Reporting and Submission of Notification Forms

Exceptions to Expedited Reporting and Submission of Notification Forms: EXPECTED Serious Adverse Events

An expedited report or notification form may not be required for specific Serious Adverse Events where the AE is **EXPECTED**. Any protocol specific reporting procedures **MUST BE SPECIFIED BELOW** and will supersede the standard Expedited Adverse Event Reporting Requirements (Note: These adverse events must still be reported through the routine reporting mechanism [i.e. Nadir/Adverse Events form]; see Footnote 1):

System Organ Class (SOC)	Adverse event/Symptoms	CTCAE Grade at which the event will not be expeditedly reported ¹
Blood and lymphatic system disorders	Anemia	3 or 4
Investigations	Platelet count decreased	3 or 4
	Neutrophil count decreased	3 or 4
	Lymphocyte count decreased	3 or 4
	White blood cell decreased	3 or 4

¹ This exception only applies if the adverse event does not result in hospitalization ≥24 hours. If this adverse event results in hospitalization ≥24 hours, then the standard expedited adverse events reporting requirements must be followed.

Specific protocol exceptions to expedited reporting should be reported expeditiously by investigators **ONLY** if they exceed the expected grade of the event.

10.42 Expedited Reporting by Investigator to Celgene

For the purpose of regulatory reporting, Celgene Drug Safety will determine the expectedness of events of being related to lenalidomide based on the Investigator Brochure. In the United States, all suspected unexpected serious adverse reactions (SUSARs) will be reported in an expedited manner in accordance with 21 CFR 312.32.

Serious adverse events (SAE) are defined above. The investigator must inform Celgene in writing using a Celgene SAE form or MEDWATCH 3500A form of any SAE within 24 hours of being aware of the event. The written report must be completed and supplied to Celgene by facsimile within 24 hours/1 business day. Fax: [REDACTED]. The initial report must be as complete as possible, including an assessment of the causal relationship between the event and the investigational product(s). Information not available at the time of the initial report (e.g., an end date for the adverse event or laboratory values received after the report) must be documented on a follow-up report. A final report to document resolution of the SAE is required. The Celgene tracking number (RV-CL-MM-PI-004334) and the institutional protocol number (MC138B) should be included on SAE reports (or on the fax cover letter) sent to Celgene. A copy of the fax transmission confirmation of the SAE report to Celgene should be attached to the SAE and retained with the patient records.

